6.1.2. Pharmacokinetic Endpoints

All PK analysis will be performed on the PK analysis set (see [Section 4](#)).

Plasma samples will be collected as specified in the SoA of the protocol and analysed for PF-07242813.

The PK parameters detailed in the [Table 2](#) will be calculated for PF-07242813 (if possible) from the concentration-time values using standard non-compartmental methods:

Table 2. Serum PK Parameters (Part 1)

Parameter	Definition	Method of Determination
Single Dose		
CC1		
$AUC_{last}(dn)$	Dose normalized AUC_{last}	$AUC_{last}/Dose$
CC1		
$AUC_{inf}(dn)^a$	Dose normalized AUC_{inf}	$AUC_{inf}/Dose$
C_{max}	Maximum serum concentration	Observed directly from data
CC1		
T_{max}	Time for C_{max}	Observed directly from data as time of first occurrence
$t_{1/2}^a$	Terminal elimination half-life	$\text{Log}_e(2)/k_{el}$ where k_{el} is the terminal phase rate constant calculated by a linear regression of the loglinear -concentration time- curve. Only those data points judged to describe the terminal log-linear decline will be used in the regression
CC1		
Multiple Doses		
$AUC\tau$	Area under the serum concentration time- profile over the dosing interval τ where $\tau=2$ weeks/336 hours	Linear/Log trapezoidal method
CC1		
C_{max}	Maximum serum concentration	Observed directly from data
$C_{max}(dn)$	Dose normalized C_{max}	$C_{max}/Dose$
CC1		

Parameter	Definition	Method of Determination
$t_{1/2}^a$	Terminal elimination half-life	$\log_e(2)/k_{el}$, where k_{el} is the terminal phase rate constant calculated by a linear regression of the loglinear -concentration time- curve. Only those data points judged to describe the terminal log-linear decline will be used in the regression
CCI		
		τ

a. If data permit.

The PK parameters in [Table 2](#) will be listed and summarized for participants in the PK parameter analysis set. Missing values will be handled as detailed in [Section 5.3.1](#). Each PK parameter will be summarized by dose and will include the set of summary statistics as specified in the table below.

Table 3. PK Parameters to be Summarized Descriptively

Parameter	Summary Statistics
AUC _{last} , AUC _{inf} , AUC τ , AUC(dn), C _{max} , C _{max(dn)} , CCI	N, arithmetic mean, median, cv%, standard deviation, minimum, maximum, geometric mean and geometric cv%.
T _{max}	N, median, minimum, maximum.
t _{1/2}	N, arithmetic mean, median, cv%, standard deviation, minimum, maximum.

There will be two summary tables presenting all PK parameters for SAD and MAD separately. They will include data from all cohorts and will be presented by dose. For the derivation of PK parameters, actual PK sampling times will be used.

To assess the relationship between the PK parameters and dose, dose normalized AUC_{inf}, AUC_{last} and C_{max} will be plotted against dose and SC or IV (using a logarithmic scale), and will include individual subject values and the geometric means for each dose. Geometric means will have a different symbol than the individual values. The values will be dose normalized (to a 1 mg dose) by dividing the individual values and raw geometric means by dose. A footnote will be added to the plots to indicate that geometric means are presented and that data from all cohorts are presented on the plot but SAD, MAD SC and MAD IV will be identified with different symbols. The SAD and MAD groups will have corresponding placebo groups throughout, if applicable. The PK data from Japanese cohort will be summarized separately.

Supporting data from the estimation of $t_{1/2}$ will be listed where applicable: terminal phase rate constant (k_{el}); goodness of fit statistic from the log-linear regression (r^2); the percent of AUC_{inf} based on extrapolation ($AUC_{extrap\%}$); and the first, last, and number of time points used in the estimation of k_{el} . These data may be included in the clinical study report.

Presentations for PF-07242813 concentrations will include:

- A listing of all concentrations sorted by subject ID, cohort (SAD or MAD), dose and nominal time postdose. The concentration listing will also include the actual times. Deviations from the nominal time will be given in a separate listing.
- A summary of concentrations by cohort, dose and nominal time postdose, where the set of statistics will include n, mean, median, standard deviation, coefficient of variation (cv), minimum, maximum and the number of concentrations above the lower limit of quantification.
- Median concentrations time plots (on both linear and semi-log scales) against nominal time postdose by cohort and dose (all treatments on the same plot per scale, based on the summary of concentrations by cohort, dose and time postdose).
- Mean concentrations time plots (on both linear and semi-log scales) against nominal time postdose by cohort and dose (all treatments on the same plot per scale, based on the summary of concentrations by cohort, dose and time postdose).
- Individual concentration time plots by cohort and dose (on both linear and semi-log scales) against actual time postdose (there will be separate spaghetti plots for each dose per scale).
- Individual concentration time plots by subject (on both linear and semi-log scales) against actual time postdose [there will be separate plots for each subject (containing all doses) per scale].

The length of time used for the x-axes of these plots will be decided on review of the data, and will depend on how long PF-07242813 concentration is quantifiable in the matrix.

For summary statistics, median and mean plots by sampling time, the nominal PK sampling time will be used, for individual subject plots by time, the actual PK sampling time will be used.

CCI

- CCI

6.2. Part 2: Atopic Dermatitis Participants

[figure not shown]
[figure not shown]
[figure not shown]
[figure not shown]
[figure not shown]
[figure not shown]
[figure not shown]
[figure not shown]
6.2.1. Secondary Endpoint (s): Percentage Change from Baseline in EASI Score at Week 6

6.2.1.1. Main Analysis

- Estimand strategy: Estimand E1 ([Section 3.1.2](#)). This estimand is intended to provide an estimate of the treatment effect in the absence of prohibited medication use in a population that may or may not be fully compliant with the treatment.
- Analysis set: mITT ([Section 4](#)) using data prepared in the description of the Primary Estimand Continuous Endpoint Set.
- Analysis methodology: Percent change from baseline will be analyzed using an ANCOVA with the observed (or imputed) Week 6 percentage change from baseline EASI score as the dependent variable with treatment arm and baseline EASI score as the independent variables.
- Intercurrent events and missing data: Data after study drug discontinuation and prohibited medication will be excluded and set to missing. Missing data which will be multiply imputed using a control-based strategy as described in ([Section 5.3.2](#)). Hundred (100) imputed datasets will be used in the analysis and results combined using PROC MIANALYZE.
- The least-squares (LS) means, the 90% confidence interval for the LS means, the difference between the LS means for each pair of treatment groups, and the corresponding 90% confidence interval will be presented for percent change from baseline in EASI score.

CCI

CCI

[figure not shown]450 and \leq 480	>480 and \leq 500	>500
Increase from baseline in QTcF (msec)	>30 and \leq 60	>60	

Categories for PR and QRS

PR (ms)	max. \geq 300	
PR (ms) increase from baseline	Baseline $>$ 200 and max. \geq 25% increase	Baseline \leq 200 and max. \geq 50% increase
QRS (ms)	max. \geq 140	
QRS (ms) increase from baseline	\geq 50% increase	

Categories for Vital Signs

Systolic BP (mm Hg)	min. $<$ 90	
Systolic BP (mm Hg) change from baseline	max. decrease \geq 30	max. increase \geq 30
Diastolic BP (mm Hg)	min. $<$ 50	
Diastolic BP (mm Hg) change from baseline	max. decrease \geq 20	max. increase \geq 20
Supine pulse rate (bpm)	min. $<$ 40	max. $>$ 120

Measurements that fulfill these criteria are to be listed in report.

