9.1. Estimands and Statistical Hypotheses

The primary estimand (for secondary endpoint EASI) will be the population average treatment effect on percent change from baseline in EASI score relative to placebo at Week 6 in the absence of prohibited medication. All observations after the initiation of prohibited medication will be set to missing. Missing data from all causes, including post-prohibited

medication use will be imputed in the PF-07242813 dose arms using a jump to control method using the distribution of the placebo group. Participants with inadequate compliance will have their recorded EASI scores used as-is in the analysis. The population based treatment effect will be the differences in the percent change from baseline in each treatment arm compared to the corresponding vehicle.

The secondary estimand **CCI** [REDACTED] will be the estimated population average treatment effect on the rates of IGA response (participants with a score of 0 or 1 and a 2 point or greater decrease from baseline) at time points specified in [Schedule of Activities](#). This is a composite estimand where success is defined as achievement of an IGA response as defined above while remaining on study, providing data and not taking prohibited medication; lack of compliance or adverse events will not be counted as a failure. The population based treatment effect will be the differences in the proportions of success in each treatment arm compared to the placebo. EASI-50, EASI-75, EASI-90 and other EASI scores will be treated in a similar manner.

CCI
[REDACTED]

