2.1.2. Secondary Estimand(s): Atopic Dermatitis Participants

Estimand E1: This estimand is intended to provide a population level estimate of the treatment effect of the study intervention on a continuous endpoint; without prohibited medications during treatment. For example:

- Study Intervention: PF-07242813 or placebo.
- Population: Participants with moderate to severe AD as defined by the inclusion and exclusion criteria.
- Variable: Percent change from baseline in EASI total score at Week 6.
- Intercurrent Events:
 - a. Prohibited medications – all scores in participants who receive prohibited medication post randomization to Week 6 will be omitted from the analysis and treated as missing scores. Missing scores will be imputed based on the assumption that participants do not benefit from the study intervention.
 - b. Inadequate compliance – participants data will be used as recorded.

Events a and b are stated with precedence in descending order.

- Population level summary: The percent change from baseline mean difference between PF-07242813 and placebo in EASI score.

[figure not shown]

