5.3.2. Efficacy Data

The following patient level data descriptions are also required for defining the pre-specified analyses:

Defined Analysis Data set (at the data level) – endpoint specific	Description
Primary Estimand Continuous Endpoint Set	
This set will include all patients in the mITT population. All data for a subject after the initiation of prohibited medications will be set to missing.
 
Note the primary estimand requires multiple imputation which will be performed on this dataset, the multiple imputations themselves will not be saved in the database, however, the SAS specifications and random number seed will be.

Secondary Estimand Categorical Endpoint Set	
This set will include all patients in the mITT population. All data for a subject after the initiation of prohibited medications, withdrawal of either study drug or the study itself will be set to a failure. Any other additional missing data will be recorded as a failure. Subjects will have either a success or failure in the dataset for all scheduled visits.

Observed Efficacy Set	
This set will include all patients in the mITT population and all observed data and includes all data recorded from the CRF pages. No data will be set to missing or modified from the original CRF record.

The primary analysis will use the primary estimand continuous endpoint set. For each landmark analysis (eg, Cross sectional analysis by week) missing data will be imputed using a control-based imputation method. PROC MI will first be called at the visit and a control-based method (implemented with the missing not at random (MNAR) option) will impute missing vehicle observations under the assumption data are missing at random (MAR) and impute missing treatment observations assuming they are similar to corresponding vehicle patients. Imputation will use the full conditional specification (FCS) method, the imputed data for the treatment and placebo arms will be combined for the analysis.

Summaries of continuous data will use the observed data only and no additional considerations are needed.

Analysis of binary data will use the Secondary Estimand Categorical Endpoint Set. This dataset by definition has no missing data since all missing values will have been set to a failure. Summaries will use the Observed Efficacy Set and will report results on an observed case (OC) basis.

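### SAP 6.2.1.1 sets EASI to missing after study drug discontinuation, a trigger found neither in Estimand E1 nor in the data set definition that the same section cites

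*SAP*

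**What the plan says.** SAP 6.2.1.1 is the main analysis of percent change in EASI at Week 6, the one endpoint on which SAP 5.1.2 bases formal inference and the verdict that the study is positive. It invokes Estimand E1, takes the Primary Estimand Continuous Endpoint Set as its data, and describes the target as the effect without prohibited medication "in a population that may or may not be fully compliant with the treatment". Its missing-data rule is then: "Data after study drug discontinuation and prohibited medication will be excluded and set to missing".

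The texts it relies on read differently:

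- **Estimand E1** (SAP 2.1.2; same rule in protocol 3.2) lists two intercurrent events. Scores are treated as missing for prohibited medication. For the other event: "Inadequate compliance – participants data will be used as recorded".
- **Protocol 9.1**: "All observations after the initiation of prohibited medication will be set to missing". It adds: "Participants with inadequate compliance will have their recorded EASI scores used as-is in the analysis".
- **SAP 5.3.2, continuous set**: "All data for a subject after the initiation of prohibited medications will be set to missing". No other trigger is given.

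For binary endpoints, the SAP 5.3.2 categorical set says that data after prohibited medication or "withdrawal of either study drug or the study itself will be set to a failure". Protocol 9.1 says of the composite response estimand that "lack of compliance or adverse events will not be counted as a failure".

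**The concern.** Two programmers could build different data sets for the only formally tested endpoint. One working from SAP 5.3.2 would keep EASI recorded after study drug was stopped; one working from SAP 6.2.1.1 would delete it.

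The deleted scores can exist. Protocol 7.1 says that stopping study intervention is not withdrawal from the study and keeps the participant under evaluation for about 70 days after the last dose. Week 6 is Day 43.

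The deletion has a direction. Under SAP 5.3.2, missing active-arm scores are imputed as if the participant resembled placebo patients, while missing placebo scores are imputed from placebo under missing at random. If the drug works, deleting an active score pulls the estimate toward no effect; deleting a placebo score mainly costs precision. This holds even if discontinuation is equally common in both arms. The analysis would then estimate something other than E1.

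**Working it through.** **Step 1. Compare the deletion triggers.**

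| Text | Prohibited medication | Study drug discontinuation |
|---|---|---|
| E1 (SAP 2.1.2, protocol 3.2) | missing | not named |
| Protocol 9.1 | missing | not named |
| SAP 5.3.2, continuous set | missing | not named |
| SAP 6.2.1.1 | missing | missing |

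The SAP may modify the protocol, but it restates E1 unchanged, and its version history lists no such change. The Appendix 6 code does not settle the matter: it imputes whatever is missing in the incoming data and does not create the missingness.

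**Step 2. Reproduce the design figure.** Inputs from protocol 9.2.2: N = 24 at 2:1 (16 active, 8 placebo), difference 50, SD 46, one-sided alpha 0.05, stated power about 80%.

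- SE = 46 × √(1/8 + 1/16) = 19.92
- Normal approximation: Φ(50/19.92 − 1.645) = Φ(0.865) = 0.807
- Noncentral t, 22 df: 0.784

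The stated figure is reproduced.

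**Step 3. Effect of deleting active-arm scores.** The documents give no discontinuation rate, so k = 0 to 4 of the 16 active participants is assumed, each with the full 50-point effect before deletion. Expected difference = 50 × (1 − k/16), a loss of 50/16 = 3.1 points per participant. The normal approximation keeps SE at 19.92. The simulation used 3000 trials, 100 imputations, normal draws from placebo, Rubin's rules and no baseline covariate.

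| k | Expected difference | Power, normal approximation | Power, simulated |
|---|---|---|---|
| 0 | 50.0 | 0.807 | 0.78 |
| 1 | 46.9 | 0.761 | 0.76 |
| 2 | 43.8 | 0.709 | 0.66 |
| 3 | 40.6 | 0.653 | 0.58 |
| 4 | 37.5 | 0.594 | 0.48 |

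**Step 4. Sensitivity for k = 1.** The result depends on the imputation draw (normal or hot-deck), on whether percent change is floored at −100%, and, with a floor, on the placebo mean, which the documents do not give. With placebo means of 0 (no floor) and −10 to −50 (floored), power for one imputed active participant ran from 0.71 to 0.77. Against about 0.78, that is a loss of 0.78 − 0.77 = 0.01 to 0.78 − 0.71 = 0.07. This range is rough: with the floor the average difference was about 35 to 45 rather than 50, so the floored runs and the 3.1-point figure describe different scenarios.

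**The case against.** The strongest reply is that very little is at stake in Cohort 9. It receives one supervised administration; once that is complete there is nothing left to discontinue, and an interrupted infusion may be restarted. SAP 6.2.1.1 also points to a data set that keeps these scores, so it is not established that the executed analysis would discard anything. The endpoint is secondary in a Phase 1 study whose primary objective is safety, and the error is conservative. The small reach and the uncertainty about execution both stand. The conservative direction is no defence: the result would still not be an estimate of E1, and the SAP would still hold two rules.

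A reader might infer several stronger things that the documents do not support:

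- *That stopping study drug is inadequate compliance, so E1 expressly keeps the data.* E1 does not name discontinuation, and neither document equates the two. What holds is narrower: no E1 rule makes these data missing.
- *That the loss falls mainly on active drug.* No reaction or discontinuation rate is given for either arm, and protocol 2.2.2 says there are no clinical safety data.
- *That one affected participant costs a definite amount of power.* One run modelled on Appendix 6 with a floor gave 0.73, and the simulation in the table gave 0.76. Both also assume a full response in someone whose dosing was stopped.
- *That Cohort 16 would be hit harder.* It is optional and its regimen is not fixed.
- *That the binary rule is simply wrong.* The protocol 9.1 summary and SAP 5.3.2 visibly disagree, but the estimand table for that endpoint is redacted in both documents, so the governing rule cannot be read. SAP 3.2.3 classes the endpoint as tertiary/exploratory.

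Protocol 9.1 does say that missing data from all causes are imputed. That governs scores that are absent; it does not license deleting scores that were recorded.

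**Conclusion.** The inconsistency is real and lies both within the SAP and between SAP 6.2.1.1 and the protocol. On the only endpoint with formal inference, SAP 6.2.1.1 adds a reason for deletion that its estimand and its own cited data set lack, without declaring a change. If it is followed, recorded Week 6 scores on active drug would be replaced by placebo-based values, with bias toward no effect if the drug works.

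The likely numerical consequence is small, because few Cohort 9 participants can be affected. The illustration of up to 3.1 points per active participant, and roughly 1 to 7 percentage points of power for the first, rests on an assumed full effect in that participant, the design SD of 46 and the chosen imputation model. It is not a forecast. The case for correcting the text rests on the conflict between the rules, not on the size of the loss.

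**What to change.** In SAP 6.2.1.1, delete the words *study drug discontinuation and*, so that data are set to missing only after prohibited medication, as in E1 and SAP 5.3.2. If the sponsor does intend discontinuation to trigger deletion, it would instead have to be added to E1 as an intercurrent event with a stated strategy in both documents, carried into SAP 5.3.2, and defined for a single-dose cohort.

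Separately, reconcile the categorical set in SAP 5.3.2 with the response definition in protocol 9.1, checking both against the unredacted estimand table before changing either.

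The cost is one phrase in the SAP plus one consistency check, with no new data collection. Both should be settled before the analysis is run.

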Appendix 2. Summary of Efficacy Analyses

Efficacy Endpoint	Analysis Type	Population	Data Inclusion and Rules for Handling Intercurrent Events and Missing Data	Analysis Model/Method
Week 6 PCFBL in EASI	Primary Analysis	mITT	MI	ANCOVA
All Visits IGA Response	Secondary Analysis	mITT	NRI	Chan and Zhang (1999) ²
All Visits CFBL PP-NRS Response	Secondary Analysis	mITT	OD	MMRM
All Visits EASI – 75 Response	Secondary Analysis	mITT	NRI	Chan and Zhang (1999) ²
CCI				
	Main analysis	mITT	All data collected will be included regardless of intercurrent events. Missing data will be imputed.	ANCOVA
	CCI			

PCFBL= Percent change from baseline; CFBL= Change from baseline; ANCOVA = Analysis of Covariance; OD = Observed data.

Appendix 3. Data Derivation Details

Appendix 3.1. Definition and Use of Visit Windows in Reporting

Visit windows will be used for efficacy variables (except change from baseline in pruritus NRS severity and frequency), and for any safety data (except the laboratory data) that display or summarize by study visit. For other endpoints (eg, ECG, vital signs, Physical Exam, Skin tolerability etc.), visit windows will be applied for summary statistics by study visits if required.

Visit No.	Visit Label	Target Day	Visit Window
	Screening	N/A	$-42 \leq \text{day} \leq -1$
1	Baseline*	1	day = 1
2	Week 1	8	$2 \leq \text{day} \leq 11$
3	Week 2	15	$12 \leq \text{day} \leq 22$
4	Week 4	29	$23 \leq \text{day} \leq 36$
5	Week 6	43	$37 \leq \text{day} \leq 50$
6	Week 8	57	$51 \leq \text{day} \leq 71$
7	Week 12	85	$72 \leq \text{day} \leq 99$
8	Week 16	113	day ≥ 100

* Baseline analysis visit window may be considered as day ≤ 1 in some analyses (eg, those involving change from baseline). That is, in case that Day 1 observation is missing, the last observation by the first dosing date may be considered as the baseline. The baseline measurements for demography, height, pre-study medical history and medications will be collected at the “Screening” visit.

If two or more visits fall into the same window, keep the one closest to the Target Day. If two visits are equaled distant from the Target Day in absolute value, the later visit should be used.

Appendix 3.2. Definition and Use of Visit Windows in pruritus NRS

Visit Label	Target Day	Visit Window
Baseline*	1	day = 1
Day 2	2	day = 2
Day 3	3	day = 3
Day 4	4	day = 4
Day 5	5	day = 5

Day 6	6	day = 6
Day 7	7	day = 7
Day 8	8	day = 8
Day 9	9	day = 9
Day 10	10	day = 10
Day 11	11	day = 11
Day 12	12	day = 12
Day 13	13	day = 13
Day 14	14	day = 14
Week 2	15	$15 \leq \text{day} \leq 22$
Week 4	29	$23 \leq \text{day} \leq 36$
Week 6	43	$37 \leq \text{day} \leq 50$
Week 8	57	$51 \leq \text{day} \leq 71$
Week 12	85	$72 \leq \text{day} \leq 99$
Week 16	113	$\text{day} \geq 100$

* Baseline analysis visit window may be considered as day ≤ 1 in some analyses (eg, those involving change from baseline). That is, in case that Day 1 observation is missing, the last observation by the first dosing date may be considered as the baseline. The baseline measurements for demography, height, pre-study medical history and medications will be collected at the “Screening” visit.

If two or more visits fall into the same window (only for Weeks 2, 4, 6, 8, 12, 16), keep the one closest to the Target Day. If two visits are equaled distant from the Target Day in absolute value, the later visit will be used.

